#### 4.2.2.2 Restrictions on diet and life style

There are no other restrictions on diet, exercise, alcohol consume or smoking except that the patient's usual habits, including nicotine and caffeine intake, should be within acceptable daily amounts in discretion of the investigator and not be drastically changed throughout the study conduct.

### 4.3 TREATMENT COMPLIANCE

Patients will be asked to bring all trial medication containers (with or without any remaining tablets/capsules) with them to each trial visit. The tablets /capsules will be counted and compliance will be calculated according to the formula:

$$\text{Compliance(\%)} = \frac{\text{Number of tablets actually taken since last tablet count}}{\text{Number of tablets which should have been taken in the same period}} \times 100\%$$

Compliance during the placebo run-in period should be between 75% and 120%. If compliance is outside this range, the patient should be carefully interviewed and, if necessary, re-informed about the purpose and the conduct of the trial. Unreliable patients should not be randomised at the discretion of the investigator.

Compliance during the randomised treatment period should be between 80% and 120%. Patients who are not compliant according to this definition should be carefully interviewed and re-informed about the purpose and the conduct of the trial.

## 5. VARIABLES AND THEIR ASSESSMENT

### 5.1 EFFICACY – PHARMACODYNAMICS

#### 5.1.1 Endpoint of efficacy

The following efficacy measures are completed at the times shown in [Section 6.2](#) and the [flow chart](#):

- Primary endpoint:
  - The primary endpoint is Neuropsychological Test Battery (NTB) response, defined as change from baseline in total z-score after 12-week treatment.

Secondary endpoints:

- Change from baseline in the ADCS-ADL (Alzheimer's Disease Cooperative Study/Activities of Daily Living) score after 12-week treatment.
- Change from baseline CDR-SB (Clinical Dementia Rating – Sum of Boxes) after 12-week treatment
- Change from baseline in ADAS-Cog11 (Alzheimer's Disease Assessment Scale-cognitive subscale) total score after 12-week treatment.

#### 5.1.2 Assessment of efficacy

Established neuropsychological assessments will be used to capture individual changes in memory, cognitive function and activities of daily living. Detailed instructions how to administer the assessments can be found in the respective user manuals which will be filed in the ISF.

#### **Neuropsychological Test Battery (NTB)**

The NTB consists of 9 validated components:

- Wechsler Memory Scale visual immediate (score range, 0-18)
- Wechsler Memory Scale verbal immediate (score range, 0-24)
- Rey Auditory Verbal Learning Test (RAVLT) immediate (score range, 0-105)
- Wechsler Memory Digit Span (score range, 0-24)
- Controlled Word Association Test (COWAT)

**Proprietary confidential information.**

© 2017 Boehringer Ingelheim International GmbH or one or more of its affiliated companies. All rights reserved.

This document may not - in full or in part - be passed on, reproduced, published or otherwise used without prior written permission.

- Category Fluency Test (CFT)
- Wechsler Memory Scale visual delayed (score range, 0-6)
- Wechsler Memory Scale verbal delayed (score range, 0-8)
- RAVLT delayed (score range, 0-30). The RAVLT delayed measure is composed of delayed recall and recognition performance components that are summed to yield a score ranging from 0 to 30.

Raw scores on each of the 9 NTB tests will be converted to z-scores using the baseline means and standard deviations (SDs) for each test. The resultant z-scores will be averaged to obtain a total z-score, incorporating all 9 NTB tests [[R13-2645](#)].

### **ADCS-ADL**

This is a rating scale used to assess basic and instrumental activities of daily living. In the full version of the scale, 23 items are rated by the investigator using information supplied by the caregiver. Each item has a score range varying from 0-3 to 0-5. The sum score could range from 0 to 78. Higher scores indicate better function [[R97-3207](#)].

**CDR-SB** is obtained through semi structured interviews of patients and informants, and cognitive functioning is rated in 6 domains of functioning: memory, orientation, judgment and problem solving, community affairs, home and hobbies, and personal care. Each domain is rated on a 5-point scale of functioning as follows: 0, no impairment; 0.5, questionable impairment; 1, mild impairment; 2, moderate impairment; and 3, severe impairment (personal care is scored on a 4-point scale without a 0.5 rating available). The CDR-SB score is computed [[R03-0748](#)].

**ADAS-cog/11** is an 11-item cognitive subscale that objectively measures memory, language, orientation and praxis with a total score range of 0 to 70 [[R96-2608](#)].

[REDACTED] has been selected as service provider to support tasks related to the neuropsychological assessments.

The services of [REDACTED] include:

- Necessary Rater prequalification
- Central Rater training for neuropsychological assessments used as primary and secondary endpoints (online and at investigator meeting)
- Provision of Rater materials
- Central Quality Review of Assessments

Details of rater prequalifications, Rater Training, Rater Materials (including Assessments) and of the Central review procedures will be available in a separate document filed in the ISF.

These members of the site staff conducting the neuropsychological assessments have to be adequately trained (either at the investigator training or individually) and training

**Proprietary confidential information.**

© 2017 Boehringer Ingelheim International GmbH or one or more of its affiliated companies. All rights reserved.

This document may not - in full or in part - be passed on, reproduced, published or otherwise used without prior written permission.

documentation has to be filed in the ISF. The training standards and standards for the conduct of the assessments will be defined for each assessment individually and can be found in the ISF. It is the responsibility of the Principal Investigator at the site to ensure proper training of all members of the site staff involved in the neuropsychological assessments.

## 5.2 SAFETY

### 5.2.1 Endpoint(s) of safety

No additional study specific important safety endpoints will be assessed in this study.

### 5.2.2 Assessment of adverse events

#### 5.2.2.1 Definitions of adverse events

##### Adverse event

An adverse event (AE) is defined as any untoward medical occurrence, including an exacerbation of a pre-existing condition, in a patient in a clinical investigation who received a pharmaceutical product. The event does not necessarily have to have a causal relationship with this treatment.

##### Serious adverse event

A serious adverse event (SAE) is defined as any AE which results in death, is immediately life-threatening, results in persistent or significant disability / incapacity, requires or prolongs patient hospitalisation, is a congenital anomaly / birth defect, or is to be deemed serious for any other reason if it is an important medical event when based upon appropriate medical judgement which may jeopardise the patient and may require medical or surgical intervention to prevent one of the other outcomes listed in the above definitions.

##### Intensity of adverse event

The intensity of the AE should be judged based on the following:

Mild:	Awareness of sign(s) or symptom(s) which is/are easily tolerated
Moderate:	Enough discomfort to cause interference with usual activity
Severe:	Incapacitating or causing inability to work or to perform usual activities

##### Causal relationship of adverse event

Medical judgment should be used to determine the relationship, considering all relevant factors, including pattern of reaction, temporal relationship, de-challenge or re-challenge, confounding factors such as concomitant medication, concomitant diseases and relevant history. Assessment of causal relationship should be recorded in the case report forms.

**Proprietary confidential information.**

© 2017 Boehringer Ingelheim International GmbH or one or more of its affiliated companies. All rights reserved.

This document may not - in full or in part - be passed on, reproduced, published or otherwise used without prior written permission.

Yes: There is a reasonable causal relationship between the investigational product administered and the AE.

No: There is no reasonable causal relationship between the investigational product administered and the AE.

If a SAE is reported from a still blinded trial, the causal relationship must be provided by the investigator for all potential trial drugs, i.e. the BI trial drug and for all other trial drugs (i.e. any active comparator or placebo according to the trial design).

#### Worsening of underlying disease or other pre-existing conditions

Worsening of underlying disease or other pre-existing conditions will be recorded as an (S)AE in the eCRF.

#### Changes in vital signs, ECG, physical examination, and laboratory test results

Changes in vital signs, ECG, physical examination and laboratory test results will be recorded as an (S)AE in the eCRF, if they are judged clinically relevant by the investigator.

#### Protocol-specified Adverse Events of Special Interest (AESI)

The following are considered as AESIs:

Hepatic injury defined by the following alterations of liver parameters:

- For patients with normal liver function at baseline:  
an elevation of AST and/or ALT  $\geq 3$  fold ULN combined with an elevation of total bilirubin  $\geq 2$  fold ULN measured in the same blood draw sample.

Patients showing these lab abnormalities need to be followed up according to [section 10.2](#) of this clinical trial protocol and the “DILI checklist” provided in the ISF.

Adverse Events of Special Interest are to be reported in an expedited manner similar to Serious Adverse Events, even if they do not meet any of the seriousness criteria – for details please see chapter [5.2.2.2](#).

#### 5.2.2.2 Adverse event and serious adverse event reporting

All adverse events, serious and non-serious, occurring during the course of the clinical trial (i.e., from signing the informed consent onwards through the follow-up-period) will be collected, documented and reported to the sponsor by the investigator on the appropriate CRF(s) / eCRFs / SAE reporting forms. Reporting will be done according to the specific definitions and instructions detailed in the ‘Adverse Event Reporting’ section of the Investigator Site File.

For each adverse event, the investigator will provide the onset date, end date, intensity, treatment required, outcome, seriousness, and action taken with the investigational drug. The investigator will determine the relationship of the investigational drug to all AEs as defined in [Section 5.2.2.1](#).

**Proprietary confidential information.**

© 2017 Boehringer Ingelheim International GmbH or one or more of its affiliated companies. All rights reserved.

This document may not - in full or in part - be passed on, reproduced, published or otherwise used without prior written permission.

If a patient reports a change in visual perception or any vision-related AE, site staff must record the patient's verbatim description in the source documents to be reported in the eCRF. A local ophthalmology assessment will be required if any visual AE that is rated as moderate or severe by the subject or at the discretion of the PI. The ophthalmologist will act as a consultant to the Investigator and may offer advice on the proper management and treatment for the reaction.

The residual effect period (REP) for BI 409306 is 7 days. Therefore, all events reported within 7 days after the last trial medication will be considered on drug. All adverse events will be reported up until the last per protocol visit (follow-up visit) which is 28 days after the last dose of trial medication. The investigator does not need to actively monitor patients for adverse events once the clinical trial has ended. However, if the investigator becomes aware of an SAE(s) that occurred after the patient has completed the clinical trial (including any protocol required REP and / or follow-up), it should be reported by the investigator to the sponsor if considered relevant.

If not stipulated differently in the ISF, the investigator must report the following events 1) if using paper process SAE form via telephone/fax or 2) if available for the trial, using the electronic submission process (RDC) immediately (within 24 hours) to the sponsor: SAEs and non-serious AEs relevant to the SAE(s), and Adverse Events of Special Interest.

BI has set up a list of AEs which are defined to be always serious. In order to support the investigator with the identification of these "always serious adverse events", if a non-serious AE is identified to be serious per BI definition, a query will be raised. The investigator must verify the description and seriousness of the event. If the event description is correct, the item "serious" needs to be ticked and an SAE has to be reported in expedited fashion following the same procedure as above.

The list of these adverse events can be found via the RDC-system.

The SAE form is to be forwarded to the defined unique entry point identified for the BI OPU (country-specific contact details will be provided in the Investigator Site File) or by using the electronic submission process. This immediate report is required irrespective of whether the investigational product has been administered or not and irrespective of causal relationship. It also applies if new information to existing SAEs or Adverse Events of Special Interest becomes available.

### Pregnancy

In rare cases, pregnancy might occur in clinical trials. Once a female subject has been enrolled into the clinical trial, after having taken study medication, the investigator must report immediately any drug exposure during pregnancy to the sponsor. Drug exposure during pregnancy has to be reported immediately (within 24 hours) to the defined unique entry point for SAE forms of the respective BI OPU (country-specific contact details will be provided in the Investigator Site File). The outcome of the pregnancy associated with the drug exposure during pregnancy must be followed up. In the absence of an (S)AE, only the

**Proprietary confidential information.**

© 2017 Boehringer Ingelheim International GmbH or one or more of its affiliated companies. All rights reserved.

This document may not - in full or in part - be passed on, reproduced, published or otherwise used without prior written permission.

Pregnancy Monitoring Form for Clinical Trials and not the SAE form is to be completed. The ISF will contain the Pregnancy Monitoring Form for Clinical Trials (Part A and Part B).

### 5.2.3 Assessment of safety laboratory parameters

All safety parameters that will be determined during the trial conduct are listed in [Table 5.2.3: 1](#). All analyses will be performed by a central laboratory. Patients don't have to be fasted for the blood sampling for the safety laboratory. The respective reference ranges and details about sample handling and shipment will be provided in the ISF (Lab Manual).

The following lab parameters will not be determined at each study visit:

- TSH, HIV and syphilis testing: at screening only
- Vitamin B12 and folate at screening and EOT only
- Urine drug screen at screening and EOT only

Table 5.2.3: 1 Safety laboratory parameters – whole blood, serum or plasma

---

**Haematology**

- Haematocrit
- Haemoglobin
  - Reticulocyte Count (reflex test if Hb outside normal range)
- Red Blood Cells (RBC) / Erythrocytes
- WBC / Leukocytes
- Platelet Count / Thrombocytes
- Differential Automatic (relative and absolute count):  
Neutrophils, Eosinophils, Basophils, Monocytes, Lymphocytes

---

**Clinical chemistry**

- Albumin
- Alkaline phosphatase
  - $\gamma$ -GT (gamma-glutamyl transferase) reflex test triggered by elevated alkaline phosphatase on two sequential measures
- ALT (alanine aminotransaminase, SGPT)
- AST (aspartate aminotransaminase, SGOT)
- Bicarbonate
- Bilirubin total, fractionated if increased
- Calcium
- Chloride
- Creatinine
- Vitamin B12
- Creatine kinase (CK)
- CK-MB, troponin (reflex tests if CK is elevated)
- Lactate dehydrogenase (LDH)
- Lipase
- Magnesium
- Phosphate
- Potassium
- Protein total
- Sodium
- Urea (BUN)
- TSH
- Folate

---

**Serology**

- HIV-antibody and Syphilis testing (Rapid plasma reagin (RPR), if RPR positive, then performing Fluorescent Treponemal Antibody test (FTA))
-

Table 5.2.3: 2 Safety laboratory parameters – urine

---

### Urinalysis

#### Semi quantitative

- Nitrite
- Protein
- Glucose
- Ketone
- Urine pH
- Leukocyte esterase (for WBC)\*

#### Urine Drug Screen

- Cannabis
- Cocaine
- Benzodiazepine
- Amphetamines
- Barbiturates
- Methadone
- Opiates
- Phencyclidine (PCP)

#### Human urine chorionic gonadotropin (HCG)

---

- Pregnancy testing (HCG, urine) will be performed in female patients of child bearing potential only according to the time points indicated in the [Flow Chart](#) or if required by local regulations more frequently or in plasma instead of urine

### 5.2.4 Electrocardiogram

ECG-recordings will be made at the time points described in the [Flow Chart](#). Twelve-lead ECGs (I, II, III, aVR, aVL, aVF, V1 – V6) will be recorded using equipment provided by a central ECG vendor. The ECGs will be recorded for at least a 10 second duration after the subjects have rested for at least 5 minutes in a supine position. Electrode placement will be performed according to the method of Einthoven/Goldberger (ankles and wrists). At all time-points, indicated in the Flow Chart, single ECGs will be recorded. ECG recordings at planned time points may be repeated for quality reasons like alternating current artefacts, muscle movements and electrode dislocation. In this case the repeated ECG recordings will be used if quality was better.

All locally printed ECGs will be evaluated by the investigator or a designee. Additional (unscheduled) ECGs can be recorded for safety reasons at any time based on the judgment of the investigator. Clinically relevant abnormal findings will be reported as baseline conditions or adverse events. Any ECG abnormalities will be carefully monitored and if necessary the subject will be removed from the trial and medically treated.

**Proprietary confidential information.**

© 2017 Boehringer Ingelheim International GmbH or one or more of its affiliated companies. All rights reserved.

This document may not - in full or in part - be passed on, reproduced, published or otherwise used without prior written permission.

All ECGs will be transmitted electronically to the central ECG vendor in order to enable a centralized and independent re-evaluation of all 12-lead ECGs (This will only be done if requested by the sponsor. Abnormalities detected during this centralised ECG evaluation will not necessarily qualify as AE.).

## 5.2.5 Assessment of other safety parameters

### 5.2.5.1 Physical examination (PE)

A physical examination will be carried out as described in the [Flow Chart](#).

A physical examination including, but not limited to, general appearance, skin, neck, eyes, ears, nose, throat, breast, lungs, heart, abdomen, back, lymph nodes, extremities, and nervous system will be performed. The physical examination will include examination of known and suspected sites of disease.

Clinically relevant abnormal findings noticed after randomisation will be reported as (S)AEs.

### 5.2.5.2 Vital signs

Vital signs (systolic/diastolic blood pressure (including orthostatic measurement as outlined below), supine pulse rate after 5 minutes rest) will be recorded at all the study visits as described in the [Flow Chart](#), including the early End of Treatment Visit and the Follow-up Visit (4 weeks after the end of treatment). Body weight will be measured at the visits indicated in the flow chart and the same scale has to be used for all measurements. The height is measured only at visit 1 (screening).

#### Measuring Orthostatic Blood Pressure

1. Have the patient lie down for 5 minutes.
2. Measure blood pressure and pulse rate.
3. Have the patient stand.
4. Repeat blood pressure and pulse rate measurements after standing 1 and 3 minutes.

Only at visit 3 the following additional vital signs measurements need to be performed which include:

- pulse rate is to be measured in a supine position after 5 minutes of rest pre-dose and at the time points of post-dose PK sampling until 90±20 minutes post-dose. Pulse rate should be taken before the respective blood for PK sampling is drawn.
- Systolic/diastolic blood pressure (including orthostatic measurement) is to be done at baseline and at 90±20 minutes post dose.

This procedure is to be performed in a quiet environment and unexpected disturbances have to be avoided. In case of an unexpected disturbance (for example slamming door) this measurement may be repeated.

Proprietary confidential information.

© 2017 Boehringer Ingelheim International GmbH or one or more of its affiliated companies. All rights reserved.

This document may not - in full or in part - be passed on, reproduced, published or otherwise used without prior written permission.

If there is a finding which meets any withdrawal criterion (See Section [3.3.4.1](#)), the subject should be removed from study participation. The investigator may repeat the additional post-dose pulse rate assessment at any other visit at the timepoints described for Visit 3 if deemed clinically necessary for any reason.

Clinically relevant abnormal findings noticed after baseline assessment will be reported as (S)AEs.

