### Clinical safety

In healthy volunteer trials [[U12-1034-01](#), [U13-1182-01](#), [U12-2165-01](#), [U13-1303-01](#), [c02098989-02](#)], the most frequent drug related adverse events were visual side effects that occurred shortly after dosing and mostly resolved within 1 h. Overall, there were no relevant changes observed for laboratory, ECG recordings, and vital signs following treatment with BI 409306 when compared to placebo. Only a rapid and short lasting increase in supine pulse rate of  $12.9 \pm 4.4$  bpm was detected in Chinese CYP2C19 poor metabolizers subjects treated with BI 409306 (100 mg single dose) in study 1289.4 [[c02098989-02](#)]. Following this observation, pharmacometric analysis of all available human data revealed a BI 409306 plasma concentration dependent increase in supine pulse rate reaching a maximum of 7-13 bpm (median) at high exposure end in CYP2C19 poor metabolizers treated with BI409306 at 100 mg. The maximum effects of BI 409306 on pulse rate were generally achieved at maximum BI 409306 plasma concentrations (20-30 minutes post dose) and disappeared rapidly with declining concentrations. Altogether, good to satisfactory safety and tolerability were observed in single doses of BI 409305 (up to 350mg in CYP2C19 extensive metabolizers (EM); up to 100mg in CYP2C19 poor metabolizers (PM)) in healthy young volunteers and multiple doses (14 days up to 100mg EM/50mg PM) of BI 409306 in healthy young and elderly subjects. None of the safety data presented a safety issue for further clinical trials.

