#### 4.1.3 Selection of doses in the trial

BI409306 has been tested in animal models to assess cognitive effects. On the basis of the described mode of action and the presented experimental efficacy in these animal memory tests, peak levels of BI 409306 in CSF in the range of 1x PDE9 IC50 need to be targeted for memory enhancing efficacy in humans. In a PoC study in healthy volunteers [[U12-2165-01](#)], it was shown that BI 409306 is able to cross the human blood-CSF barrier (plasma to CSF) with a concentration corresponding to IC 50 (65 nmol/L) in CSF reached at 25 mg in 2 out of 4 subjects and exceeded IC 50 in all subjects at the higher doses. CSF exposure to BI 409306 increased with increasing dose and the CSF to plasma ratio for BI 409306 Cmax in humans is comparable to the one observed in rats and is constant over the entire dose range tested. CSF concentration-time profiles of BI 409306 peak approximately 0.5 to 1 hour later than in plasma and decline monoexponentially and roughly in parallel to plasma concentrations afterwards with BI 409306 concentrations in CSF decreasing beyond the quantification limit (0.5 nmol/L) after 8 to 14 hours post dosing. Therefore, the 25mg dose is anticipated to be the

Proprietary confidential information.

© 2017 Boehringer Ingelheim International GmbH or one or more of its affiliated companies. All rights reserved.

This document may not - in full or in part - be passed on, reproduced, published or otherwise used without prior written permission.

effective dose and will be tested once daily (QD) and twice daily (BID). To study the dose-response relationship, a lower dose (10mg) and a higher dose (50mg) will also be tested. For further details to the preclinical data as well to the human proof of mechanism study, please refer to the current version of the IB.

Following the run-in period patients will be randomised (Visit 3) to one of the 5 treatment arms.

Patients who qualify will be randomised to one of five treatment groups as follows:

- BI 409306 10mg QD (Treatment Group 1)
- BI 409306 25mg QD (Treatment Group 2)
- BI 409306 50mg QD (Treatment Group 3)
- BI 409306 25mg BID (Treatment Group 4)
- Placebo (Treatment Group 5)

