## 6. INVESTIGATIONAL PLAN

### 6.1 VISIT SCHEDULE

All trial visits should preferentially take place in the morning starting before 9:00 AM. Patients should be instructed not take trial medication on the morning of a clinic visit before attending the clinic.

All patients are to adhere to the visit schedule as specified in the [Flow Chart](#) (with time window for rescheduling).

If any visit has to be rescheduled, subsequent visits should follow the original visit date schedule. The trial medication packs contain sufficient medication to allow for these time windows.

The end of the trial is defined as “last patient out”, i.e. last visit completed by the last patient.

If the reason for removal of a patient from the treatment is an adverse event or an abnormal laboratory test result, the patient must be followed until complete resolution or stabilization of the event or until follow-up is agreed adequate by the Investigator and BI Clinical Monitor.

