### Visits 5, 6 and EOT/ED

- Study procedures have to be completed according to the [Flow Chart](#).
- Collect returned medication at every visit prior to dispensing new medication
- Neuropsychological assessments and collection of urine and blood for laboratory testing [REDACTED] must be performed prior to administration of study medication
- For diabetic patients with antidiabetic therapy: exclusion of hypoglycemia for the period of the neuropsychological assessment (documented plasma glucose concentration  $\geq 90$  mg/dl (5mmol/l) at the beginning and directly after the assessment).
- Administer the following neuropsychological assessments in the following order:
  - CDR-SB (V5 and EOT)
  - NTB (V5 and EOT)
  - ADCS-ADL (EOT)
  - ADAS-cog11 (EOT)
- Administration of C-SSRS (baseline since last visit scale)
- The intake of trial medication and handling of medication blisters should be discussed and (if deemed necessary) re-trained with the patient and the caregiver. The dose of trial medication should be taken by the patient after the neuropsychological assessments have been administered.
- [REDACTED]
- Blood pressure must always be measured before taking any blood sample
- Laboratory samples will be collected as described in [Flow chart](#).
- New medication kit must be dispensed at Visits 5 and Visit 6 and IRT must be contacted at those visits to obtain medication kit numbers to be dispensed.
- Instruct patient NOT to take study medication on the morning of next trial visits.
- Visit EOT/ED is the end of treatment visit. Study medication will not be taken at Visit EOT/ED.

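### After Day 1 no required pulse reading, and at no visit an ECG, is timed to the 20-30 minute post-dose peak of the pulse effect that the protocol describes

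*Protocol*

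**What the plan says.** **The effect.** Protocol 1.2 (Clinical safety) reports a pulse increase that depends on plasma concentration, with a median maximum of 7-13 bpm at the high-exposure end in CYP2C19 poor metabolizers given 100 mg. Its maximum was "generally achieved at maximum BI 409306 plasma concentrations (20-30 minutes post dose) and disappeared rapidly with declining concentrations".

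**Post-dose pulse.** Protocol 5.2.5.2: "Only at visit 3 the following additional vital signs measurements need to be performed". Section 6.2.2 gives the Visit 3 windows as 15-25, 25-35, 35-55 and 70-110 minutes. The investigator may repeat the series at another visit if it is judged clinically necessary.

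**Visit days.** Protocol 6.1: "Patients should be instructed not take trial medication on the morning of a clinic visit before attending the clinic". Under 4.1.4 the drug is taken during the visit, under supervision, after blood is drawn. At Visits 5, 6 and EOT (6.2.2), neuropsychological tests and blood and urine collection "must be performed prior to administration of study medication", and "Blood pressure must always be measured before taking any blood sample". No drug is taken at EOT.

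**ECG.** Protocol 5.2.4 says that "single ECGs will be recorded" at the Flow Chart visits. Neither 5.2.4, nor the Flow Chart, nor 6.2.2 places an ECG before or after the dose.

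**Withdrawal criteria.** Protocol 3.3.4.1 defines its heart-rate criteria by minutes after a dose and does not limit them to the first dose.

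**The concern.** The effect is short and follows plasma concentration, so a reading can show it only if taken soon after a dose. The plan uses that fact on Day 1 and then stops. From Visit 5 onward the order of procedures puts routine vital signs ahead of the dose, and the ECG carries no dose-relative time at all, even at Visit 3.

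Safety is half of the primary objective (2.2), and 7.3.3 has vital signs and ECGs assessed for change over the course of the trial. If the later readings are taken at low exposure, tables for active drug and placebo can look alike whatever happens at peak. A reader of the report could take this as evidence about repeated dosing that the measurements cannot give.

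**Working it through.** No sample size or power figure is involved. The check sets the assessment schedule against the stated peak.

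1. **Visit 3 coverage.** The first two windows, 15-25 and 25-35 minutes, together span 15-35 minutes and contain the whole 20-30 minute peak. The 90±20 minutes in 5.2.5.2 is 90 − 20 = 70 to 90 + 20 = 110, the same as the last window in 6.2.2. Day 1 pulse is covered and the two sections agree.

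2. **Visits 5 and 6, vital signs.** Blood pressure precedes any blood sample (6.2.2), and blood precedes the dose (4.1.4, 6.2.2). Blood pressure is therefore pre-dose. Step 2 of the orthostatic procedure in 5.2.5.2 takes pulse together with blood pressure, so the paired pulse is pre-dose as well.

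3. **Exposure at those readings.** Assume regular morning dosing, or morning and evening dosing for BID. The last active dose is then about 24 h earlier in the QD arms and about 12 h earlier in the BID arm. Protocol 4.1.3 describes CSF concentrations, falling roughly in parallel with plasma, as "decreasing beyond the quantification limit (0.5 nmol/L) after 8 to 14 hours post dosing". So 24 h lies beyond that range and 12 h lies inside it.

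4. **EOT and Visits 4a-c.** No dose is taken at EOT. At Visits 4a-c no safety blood sample or neuropsychological test is scheduled, so the ordering argument in step 2 does not apply. Timing there is unspecified; it is not shown to be pre-dose.

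5. **ECG count.** The Flow Chart schedules ECGs at Visits 1, 3, 4a, 4b, 4c, 5, 6, EOT and FU, which is 9. Visit 1, EOT and FU involve no dose of randomised drug: 9 − 3 = 6 at most. If 4b and 4c become phone contacts, 6 − 2 = 4. ECGs with a stated time relative to dose: 0.

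6. **Pulse coverage.** Dosing days: 12 × 7 = 84. Mandatory post-dose pulse: 1/84 = 1.2% of dosing days, or 1/168 = 0.6% of doses in the BID arm. Mandatory post-dose series after Day 1: 0. Planned patients on active drug: 4 × 59 = 236.

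7. **3.3.4.1 against 5.2.5.2.** The criteria are expressed in minutes post-dose with no restriction to the first dose. The only required readings on that clock are at Visit 3. SAP Table 6.2:1 (code E2) makes failure to discontinue under these criteria an important protocol violation, identified automatically. The documents do not say at which visits the criteria are to be assessed.

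**The case against.** The strongest reply is that Day 1 is the right place to look and is covered well. Pulse is mandatory across the peak after the first randomised dose, a withdrawal rule acts on it, and SAP 6.1 counts time from first intake as on treatment. With CSF levels below quantification by 8-14 h there should be little carry-over between QD doses, so the first peak is a fair proxy for later ones. Section 1.2 reports 14-day dosing in healthy young and elderly subjects and no safety issue for further trials. Moderate and strong CYP1A2 inhibitors are prohibited (4.2.2.1). The investigator may repeat the series, and adverse events are collected at every visit.

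Much of this stands. A reader might infer that on-treatment monitoring misses the pulse effect altogether. It does not, because of Visit 3. Nor do the documents support applying 7-13 bpm to the 236 active patients: that figure is for poor metabolizers at 100 mg, and the largest single dose here is 50 mg. They do not label this a cardiac risk of special interest either; the only AESI is hepatic injury (5.2.2.1).

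The reply leaves three gaps.
- It covers pulse only. No ECG is tied to a dose on Day 1 or later.
- The proxy argument assumes that exposure stays as it was on Day 1, over 12 weeks in older patients. The prior multiple-dose experience cited is 14 days in healthy subjects.
- The optional repeat needs a prompt. Symptoms, a borderline Visit 3 reading or a medication change could give one; a pre-dose reading at Visit 5 or 6 is unlikely to.

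Part of the PK schedule is redacted, including material for Visit 6, so other post-dose contact at that visit cannot be judged.

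**Conclusion.** The point holds in a limited form. After Day 1 no required pulse reading is timed to the stated peak, and 0 of up to 6 dosing-day ECGs have a time relative to dose. Peak effects under repeated dosing, and any ECG effect at peak, would be seen only through adverse events, discretionary repeats or chance timing. Unremarkable Week 4-12 vital signs and ECGs could not support a statement of no peak effect. No document commits the sponsor to such a statement, since safety analysis is descriptive, so what is at stake is how the tables may be read.

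The conclusion rests on the visible text, on pulse being taken with blood pressure as the orthostatic procedure describes, and on regular dosing intervals. It does not extend to Visits 4a-c, where timing is simply not stated. It does not touch the efficacy analysis. This is a cheap improvement to the safety data, not a failure of the design.

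**What to change.** **ECG timing.** In 5.2.4, the Flow Chart and 6.2.2, tie the ECGs already scheduled at Visits 5 and 6 to the supervised in-clinic dose, at a post-dose time that the sponsor chooses to cover its own stated peak. Record the interval from dose to ECG, and state in the SAP that ECG heart rate is reported by time since dose. The ECG is already taken supine after 5 minutes' rest, so it yields heart rate and rhythm together. Vital signs and the neuropsychological order can stay as they are.

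**Reconciliation.** 3.3.4.1 (criteria in minutes post-dose, not limited to the first dose) and 5.2.5.2 (post-dose readings required only at Visit 3) must be reconciled by stating at which visits the criteria are assessed. No dose, threshold or withdrawal rule is proposed.

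**Cost.** Amendment wording and about 30 minutes more at two visits, with no added procedure. There is one statistical drawback: these ECGs would no longer share a dose-relative time with the Visit 3 ECG, which is untimed and may be pre-dose. Change from baseline would then mix drug effect with timing, so the comparison with placebo at the same post-dose time should carry the interpretation.
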